Interestingly, Gulf War veterans with pain symptoms often meet the criteria for fibromyalgia, strongly suggesting an overlap in not only pain symptoms but also in the mechanisms of action. Current treatment options for Gulf War Illness are as diverse as their outcomes. Both pharmacological and non-pharmacological modalities are currently used, but only a small subset of patients benefit and most of the patients remain noncompliant to treatment. As current treatment options generate only moderate improvement, modification of cortical physiology by non-invasive brain stimulation would be a valuable and novel therapeutic approach. Our group has developed a new treatment option using transcranial Direct Current Stimulation (tDCS) for the management of pain in patients with Fibromyalgia (Plazier et al., 2014; Plazier et al., 2015). We demonstrated in a recent study published in Neuromodulation (N = 10) and a follow-up clinical trial published in Brain Stimulation (N = 45) that direct stimulation of some nerves at the back of the head (i.e. the occipital nerve field) of fibromyalgia patients seems to cause an overall beneficial effect on general bodily pain (e.g. bone and joint pain) symptoms and confirmed additional improvement on participants' tender points, quality of life, fatique, and sleep quality (Plazier et al., 2014; Plazier et al., 2015). This effect was maintained within a six-month follow up period. Seventy-six percent of the patients were satisfied or very satisfied with their treatment and 56% of the patients were able to return to work. We further showed that transcranial direct current stimulation (tDCS) can be used to non-invasively modulate these nerves at the back of the head (i.e. occipital nerve field), producing similar results ([name] et al., 2011). Our study showed that stimulation of these nerves at the back of the head (i.e. occipital nerve field) using tDCS over 10 sessions decreased bone and joint pain symptoms by 30% in comparison to baseline and 22% in comparison to sham stimulation in patients diagnosed with fibromyalgia (see figure 4, middle)(Plazier et al. 2015c). These findings are further confirmed by our recent pilot study (N = 15) performing 10 sessions of tDCS targeting the nerves at the back of the head (i.e. occipital nerve field), showing pain suppression of 21% and fatigue suppression of 25% for more than 6 months. In another study by our group, we also showed that this stimulation set up has a direct impact on the latencies of the Laser Evoked Potential (Plazier et al., 2015) and confirmed its impact on joint/muscle pain symptoms in patients with fibromyalgia.

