Resting state EEG. The EEG procedure is a non-invasive technique that will record brain electrical activity while the participant sits quietly in a chair for 5 minutes with their eyes are closed. In order to do that, a cap with 64 electrodes will be placed on the scalp. The cap is similar to a loose nylon swim cap. The cap will be placed on the participant's head and then a small amount of a salt water mixture will be added to each electrode from the outside of the cap. The cap placement will take up to 30 minutes. This is a common clinical procedure carried out in neurology.

Session 2-10: tDCS stimulation (approximately 45 minutes)

tDCS Stimulation - Participants will be randomly assigned to two different groups after they have finished assessment: the first group will receive real tDCS targeting the occipital nerve field. This group will receive 20 minutes of stimulation targeting the occipital nerve field area consisting of a current of 1.5mA. The second group (sham, or control, group) receive the same procedure for tDCS but with no delivery of electrical current. For both groups, the stimulation current will gradually ramp up to 1mA during the first 60 seconds of stimulation but the current will only persist for real tDCS group.

Session 11: tDCS stimulation + Immediate Post-tDCS Assessment (approximately 3.5 hours)

tDCS Stimulation - Participants will receive tDCS for 20 minutes (1) at 1.5 mA targeting the occipital nerve field area, or

Last Revised 01/2016 Page 14 of 22

(2) with no delivery of electrical current (sham, or control, group). For both groups, the stimulation current will gradually ramp up to 1mA during the first 60 seconds of stimulation but the current will only persist for real tDCS group.

Immediate Post-tDCS Assessment - Participants will complete the following assessments that were part of the Pre-tDCS assessment:

- 1. VAS. The Visual Analogue Scale
- 2. MFIS. Modified Fatigue Impact Scale
- 3. PSQI. Pittsburgh Sleep Quality Index
- 4. BDI. Beck Depression Inventory
- 5. PCS. Pain Catastrophizing Scale
- 6. MGPQ. McGill Pain Questionnaire
- 7. PVAQ. Pain Vigilance and Awareness Questionnaire
- 8. Resting state EEG.

Sessions 12 (1 week after), 13 (4 weeks after), 14 (12 weeks after) and 15 (24 weeks after) - Post Assessments (approximately 2.5 hours):

Post-assessments will take place at 1 week after, 4 weeks after, 12 weeks after and 24 weeks after the last tDCS session. Follow up-tDCS Assessment are:

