### 3. Sample Size and Power

- **Primary Outcome:** Pain severity on the Visual Analogue Scale (VAS).
- **Secondary Outcomes:** Questionnaire measures (MFIS, PSQI, BDI, PCS, MGPQ, PVAQ) and neurophysiological measures (LEP, EEG, rsfMRI).
- **Sample Size:** 60 participants (30 per group), allowing an 80% power to detect a 1.1 cm difference on the VAS scale (Cohen's d effect size) with a significance level of 0.05. The design anticipates a 10% dropout rate.

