### 6. Statistical Analysis Plan

#### A. Primary Outcome Analysis: Pain Severity (VAS)

- **Modeling:** Mixed-effects repeated-measures ANOVA with group (treatment vs. sham) as a between-subjects factor and time (baseline, immediate post-treatment, 4-week, 12-week, 24-week) as a within-subjects factor.
- **Post-Hoc Tests:** Bonferroni-adjusted post-hoc tests will examine specific time points if interaction effects are significant.
- **Intention-to-Treat (ITT) and Per-Protocol Analyses:**
  - **ITT:** Last observation carried forward (LOCF) for missing data.
  - **Per-Protocol:** Include only participants with at least 8 out of 10 therapy sessions completed and no interfering medications.

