## 9. Handling Missing Data and Sensitivity Analysis

- **Imputation:** Apply multiple imputation if the missing rate is above 10%.
- **Sensitivity Analysis:** Compare results with and without LOCF to ensure robust findings.

This statistical plan aligns with the study objectives and incorporates the additional neurophysiological and data management details.

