**Deviation statistical plan:**

The study was unfortunately disrupted due to the impact of COVID-19, which led to its discontinuation. Consequently, we have been limited in our ability to collect and analyze comprehensive data, and are currently only able to report descriptive statistics. We acknowledge that this is a limitation in our findings, and we are exploring potential avenues to resume the study and gather more robust data in the future.

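### Primary VAS analysis: LOCF plus an undefined 10% trigger for multiple imputation leaves the missing-data method open, and LOCF can bias the week-24 contrast in either direction

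*SAP*

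**What the plan says.** SAP Section 6A analyses the VAS with a mixed-effects repeated-measures ANOVA (group by time, five visits from baseline to 24 weeks). Its ITT rule carries no condition: "Last observation carried forward (LOCF) for missing data". Single visits are reached only through the interaction: "Bonferroni-adjusted post-hoc tests will examine specific time points if interaction effects are significant".

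Section 9 adds a second rule, "Apply multiple imputation if the missing rate is above 10" percent, and a check, "Compare results with and without LOCF to ensure robust findings". It does not say how the rate is counted, whether imputation then replaces LOCF in the ITT analysis, which imputation model is used, or what the analysis without LOCF is.

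Section 3 puts expected attrition at the same figure as the trigger: "The design anticipates a 10% dropout rate".

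The protocol's visit schedule has one more VAS than the SAP's time factor: "Post-assessments will take place at 1 week after, 4 weeks after, 12 weeks after and 24 weeks after the last tDCS session". The 1-week score does not appear in SAP Sections 4 or 6A.

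**The concern.** There are two problems.

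First, an SAP should fix the missing-data method before anyone sees the data. Here the method above the threshold depends on a rate that can reasonably be counted by participants, by week-24 scores, by post-baseline scores or by all scores, and these counts can fall on opposite sides of 10%. An analyst could pick the count after seeing the results.

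Second, LOCF enters an earlier score as though it had been measured 24 weeks after a two-week treatment. The trial's aim is long-term relief, so the late contrasts matter. LOCF is neutral only under particular patterns of effect and dropout. It overstates durability if relief fades. It understates a lasting effect if participants leave before any post-treatment score, because baseline is then carried forward. The model named in Section 6A does not need it, since a mixed model can be fitted to incomplete records.

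**Working it through.** **1. The plan's own figure.** Section 3 gives 1.1 cm, 30 per group, 80% power and a significance level of 0.05, but no SD and no sidedness. The sample size therefore cannot be reproduced; only the implied SD can be recovered. Taking the test as two-sided, the detectable standardised difference is (1.960 + 0.842) x sqrt(2/n).

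- n = 30: 0.723, so SD = 1.1/0.723 = 1.52 cm (1.50 with the t distribution).
- n = 27 (30 less 10%): 0.762, so SD = 1.1/0.762 = 1.44 cm (1.42 with t).

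SDs of 1.42 and 1.52 cm are used below for error rates. The bias figures do not depend on the SD.

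**2. What the 10% rule does under different counts.** There are 60 participants, 60 x 4 = 240 post-baseline scores and 60 x 5 = 300 scores in all. Assume leavers split equally before the 4-, 12- and 24-week visits, so they miss three, two and one scores.

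| Leavers | Missing scores | Of participants | Of 240 | Of 300 |
|---|---|---|---|---|
| 6 (2/2/2) | 2x3 + 2x2 + 2x1 = 12 | 10.0% | 5.0% | 4.0% |
| 12 (4/4/4) | 4x3 + 4x2 + 4x1 = 24 | 20.0% | 10.0% | 8.0% |

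With 12 leavers the rule is triggered on the participant count and not on either score count (10.0% is not above 10%). Counting week-24 scores gives the same result as counting participants here.

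Chance that the rule triggers, with dropout random and spread over follow-up:

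| True dropout | Participants | Post-baseline scores | All scores |
|---|---|---|---|
| 10% | 39% | 1.4% | 0.1% |
| 20% | 97% | 45% | 17% |

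The participant figures are exact binomial: P(7 or more of 60) = 0.394 at 10% and 0.969 at 20%. The score-based figures come from 200,000 simulated trials.

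**3. LOCF bias at week 24.** With equal dropout in the arms, bias = sum over dropout times of (share leaving) x (effect at last observed visit - effect at week 24). The effect is the reduction in VAS against sham, so a positive bias favours tDCS. The trajectories are assumptions.

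- Complete fading (1.1, 0.825, 0.55, 0 cm at post-treatment, 4, 12, 24 weeks), 10% spread equally: 0.10 x (1.1 + 0.825 + 0.55)/3 = +0.0825 cm. All leaving right after the post-treatment visit: 0.10 x 1.1 = +0.11 cm. At 20%, if LOCF still applies: +0.165 to +0.22 cm.
- Half fading (1.1 to 0.55 cm): +0.04 to +0.055 cm at 10%.
- Sustained 1.1 cm, dropout after the post-treatment visit: 0.
- Sustained 1.1 cm, dropout before any post-treatment score: 0.10 x (0 - 1.1) = -0.11 cm.

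Unequal dropout can bias the contrast with no treatment effect at all. If both arms worsen by 1.0 cm after the post-treatment visit, and 20% of one arm and 5% of the other leave right after that visit, the bias is 0.20 x 1.0 - 0.05 x 1.0 = 0.15 cm in favour of the arm that lost more.

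**4. False week-24 claims under LOCF.** Complete fading, 30 per arm, correlation 0.3 to 0.7, 20,000 simulated trials per setting. The SAP does not say how many tests share the Bonferroni adjustment; four visits are assumed, giving 0.05/4 = 1.25%.

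- 10% dropout: 5.3 to 6.4% unadjusted; 1.3 to 1.8% at the 1.25% level (0.9 to 1.8% when the interaction must be significant first).
- 20% dropout, LOCF retained: 1.8 to 4.0% at the 1.25% level.

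**5. The alternative.** REML on observed values (SD 1.42 cm, correlation 0.5, compound symmetry, 3,000 trials per setting) gave bias within 0.011 cm and error of 0.8 to 1.3% at the 1.25% level. The week-24 standard error was 0.379 to 0.382 cm at 10% dropout, against about 0.367 cm under LOCF.

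**The case against.** The strongest case is that the consequence is small and the gap narrow.

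- **Week 24 is not the primary test.** It is one of several post-hoc contrasts behind the group-by-time interaction. With no effect at any visit and equal random dropout of 10 to 20%, the interaction test on LOCF data rejected in 4.6 to 5.6% of simulated trials, so there is no visible inflation. The false claims in step 4 arise only where tDCS truly works at end of treatment; they overstate how long relief lasts. This stands and limits the point to claims of durability.
- **The bias is small at planned dropout.** 0.08 to 0.11 cm is under a third of the 0.37 cm standard error, and it assumes complete fading. The protocol's earlier work in fibromyalgia points the other way ("This effect was maintained within a six-month follow up period"), and it also reports a tDCS pilot with relief beyond six months. Under sustained relief and equal post-treatment dropout the bias is zero. This stands, but it is an expectation from another population, and durability is what the trial sets out to test.
- **At exactly six leavers all counts agree.** None exceeds 10%, so LOCF applies. True, but at a 10% risk the participant count still crosses the line 39% of the time.
- **The SAP is consistent on visits.** Sections 4 and 6A list the same five. What remains open is whether the protocol's 1-week score may be carried forward or counted.
- **Section 9 compares results with and without LOCF.** That helps, but it names neither the other analysis nor which result is primary.
- **The REML result is favourable by construction.** Dropout was random in those simulations. This is fair, and it is the reason for a not-at-random sensitivity analysis.

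**Conclusion.** The concern holds. LOCF is the unconditional ITT rule, the multiple-imputation rule has no defined rate and no stated precedence, and the expected dropout sits on the threshold. Below the threshold the plan is clear (LOCF); above it, the primary method is not determined.

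Under the stated assumptions (1.1 cm at end of treatment, equal dropout), LOCF bias at week 24 runs from -0.11 to +0.11 cm at 10% dropout, or up to a tenth of the target difference. Under complete fading it reaches +0.22 cm, a fifth, at 20% if LOCF is kept. Neither sign nor size is known in advance. At 10% dropout the effect on type I error is small.

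This should be fixed but is not fatal. The SAP's closing deviation statement says the study was discontinued and only descriptive statistics can be reported for now, but also that "we are exploring potential avenues to resume the study". The point matters for a resumed study or any inferential analysis.

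**What to change.** In Section 6A, replace the LOCF line with wording such as: *The ITT analysis fits the mixed model (group, time, group x time) by REML to all observed VAS values of all randomised participants, with no single imputation.* Name the covariance structure, and state whether the 1-week VAS enters the model.

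In Section 9, delete the 10% trigger. Run multiple imputation as a prespecified sensitivity analysis whatever the missing rate, with its imputation model stated, and include one not-at-random version (sham-referenced imputation is one option). Keep LOCF, if at all, as a labelled supplementary result.

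The cost is SAP wording and a little more analysis, with no extra participants or data. The week-24 standard error is about 3 to 4% larger than under LOCF at 10% dropout (0.379/0.367 = 1.03; 0.382/0.367 = 1.04) and 7 to 9% larger at 20%. REML assumes data are missing at random, which the not-at-random analysis is there to test.

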## B. Secondary Outcome Analysis

- **Questionnaires:** MFIS, PSQI, BDI, PCS, MGPO, and PVAQ will be assessed using repeated-measures ANOVA to evaluate time × group interactions.
- **Neurophysiological Markers:**
  - **LEP:** N2P2 amplitude and latency will be assessed using repeated-measures ANOVA to evaluate group (treatment vs. sham) × time (baseline vs. immediate post-treatment) interactions. Correlations between VAS changes and N2P2 amplitude differences will be analyzed with Pearson correlations.
  - **EEG:** sLORETA contrast maps will analyze voxel-by-voxel comparisons (pre- vs. post-tDCS) to determine active vs. sham differences. Randomized statistical thresholding (5000 permutations) will correct for multiple comparisons.
  - **rsfMRI:** Seed-based functional connectivity analyses will target key regions (dACC, pgACC, amygdala, and insula). Group-level comparisons (treatment vs. sham) will assess changes from baseline to post-treatment and correlate with VAS scores to evaluate pain reduction prediction.

## 7. Exploratory Analysis

- **Correlation Analyses:** Correlate rsfMRI connectivity changes and EEG contrast map changes with VAS pain reduction to identify neurophysiological predictors of pain relief.

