The goal of this proposal is to produce long-term modulation of pain pathways leading to a suppression of pain symptoms in Gulf War Illness patients with pain symptoms by delivery of 10 daily sessions (1 session a day, 5 weekdays a week, for a 2 week period) of transcranial Direct Current Stimulation (tDCS) over specific nerves at the back of the head (i.e. the occipital nerve field (C2)). After identifying Gulf War illness patients with pain symptoms using standard measures, we will address the following specific aims:

Aim 1. Produce long-term modulation of pain pathways reflected in a suppression of pain symptoms by administering repeated sessions of real tDCS targeting the greater occipital nerve at the back of the head.

Hypothesis #1: pain symptoms detectable in measures of pain symptoms (e.g. Visual Analogue Scale and other pain scales) will be improved after repeated sessions of real tDCS when compared to sham tDCS.

Aim 2. Produce long-term modulation of pain pathways reflected in resting state Electroecephalography (EEG) after administering repeated sessions of real tDCS targeting the greater occipital nerve at the back of the head.

Hypothesis # 2: EEG resting state activity changes in both the ascending pathways and descending pathway correlate with suppression of pain. A decrease in activity in the pregenual Anterior Cingulate Cortex (ACC), dorsal Anterior Cingulate Cortex (dACC), insula, and somatosensory cortex after the procedure will be less strongly correlated with pain in comparison to the baseline measurement.

Describe previous studies that form the basis for the proposed research:

Gulf War Illness is a chronic and multisymptomatic disorder affecting returning military veterans of the 1990-1991 Gulf war. Pain is a major complaint of Gulf War Illness patients and is a leading cause of disability in veterans diagnosed with musculoskeletal ailments including joint and muscle pain, muscle fatigue, difficulty with lifting objects, and extremity paresthesia's. As a result, the target of the present proposal is the treatment of the pain symptoms, as this is detectable across all Gulf War Illness case classification systems.

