**Title: Transcranial Direct Current Stimulation for Pain Treatment in Gulf War Illness**

**NCT03312920**

**Date: June 20/2017**

## Statistical plan:

### 1. Study Overview and Objectives

The study evaluates the efficacy of transcranial Direct Current Stimulation (tDCS) for managing pain in Gulf War Illness (GWI) veterans. The specific objectives are to determine if tDCS targeting the occipital nerve reduces pain and to identify EEG and rsfMRI-based markers that correlate with pain relief.

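### The planned marker–pain correlations name no treatment-arm term, so if pooled they can show a link that only reflects an arm effect on both measures

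*SAP*

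**What the plan says.** SAP section 1 makes it one of two specific objectives to "identify EEG and rsfMRI-based markers that correlate with pain relief". Three later statements carry this out.

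- **LEP (SAP 6B):** "Correlations between VAS changes and N2P2 amplitude differences will be analyzed with Pearson correlations".
- **rsfMRI (SAP 6B):** the treatment-versus-sham group comparisons "will assess changes from baseline to post-treatment and correlate with VAS scores to evaluate pain reduction prediction".
- **rsfMRI and EEG (SAP 7):** changes in both markers are correlated with the fall in VAS pain "to identify neurophysiological predictors of pain relief".

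Arm does appear in section 6B, but in the marker comparisons: a group by time ANOVA for LEP, the group-level contrast for rsfMRI, and for EEG "sLORETA contrast maps will analyze voxel-by-voxel comparisons (pre- vs. post-tDCS) to determine active vs. sham differences". No arm term, stratification or within-arm analysis is named for any correlation with VAS. Section 7 does not give the visit at which VAS reduction is taken.

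Hypothesis #1 in the protocol's objectives expects that pain "will be improved after repeated sessions of real tDCS when compared to sham tDCS". Aim 2 expects real tDCS to modulate resting-state EEG, and Hypothesis #2 expects the EEG changes to correlate with pain suppression. Hypothesis #2 names no arm term either.

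**The concern.** Pooling two randomised arms mixes two sources of association. One is the link between marker change and pain change among patients treated alike, which is what a marker of pain relief should mean. The other is the difference between arms: if active tDCS moves both averages, the two clouds of points are displaced along a diagonal, and the pooled correlation is non-zero even when each cloud is round. The protocol hypothesises this situation.

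The trial could then name a marker as tied to pain relief when it has only measured the arm difference a second time. Calling that marker a *predictor* goes further, because the plan correlates change with change and designates no marker measured before the pain outcome.

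**Working it through.** **Inputs.** From SAP section 3: 30 per group, 80% power, a 1.1 cm VAS difference, significance level 0.05, 10% dropout. Not in the documents: the VAS SD, a value of d, sidedness (two-sided assumed), and any expected arm effect on a marker.

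**1. The plan's own figure.** The sample size cannot be reproduced without an SD, so I back-solved the effect. In the normal approximation, d = √(2/n) × (1.960 + 0.842).

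- n = 30: d = 0.2582 × 2.802 = 0.72. The noncentral t gives 0.74, implying SD = 1.1/0.736 = 1.50 cm.
- n = 27 (30 × 0.9): d = 0.2722 × 2.802 = 0.76. The noncentral t gives 0.78, implying SD = 1.1/0.777 = 1.42 cm.

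Reading 1.1 as Cohen's d itself would give about 99% power at 30 per group, which does not match 80%. I use d = 0.78 for VAS as a working assumption; at 30 per arm it corresponds to 84% power.

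**2. Expected pooled correlation with no within-arm link.** Let dV and dM be the arm effects on VAS change and marker change, in within-arm SDs. With 1:1 allocation,

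r = (dV·dM/4) / √[(1 + dV²/4)(1 + dM²/4)].

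For dV = 0.78, 1 + dV²/4 = 1.1521.

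- dM = 0.3: 0.0585/√(1.1521 × 1.0225) = 0.05
- dM = 0.5: 0.0975/√(1.1521 × 1.0625) = 0.09
- dM = 0.78: 0.1521/1.1521 = 0.13
- dM = 1.0: 0.195/√(1.1521 × 1.25) = 0.16

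These are sizes. The sign follows the directions of the two effects.

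**3. Rejection rate of a single two-sided 5% Pearson test.** Simulation of 40,000 bivariate-normal trials per setting, within-arm correlation zero:

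| dV | dM | Pooled, 27 per arm | Pooled, 30 per arm | Arm-adjusted |
|---|---|---|---|---|
| 0.78 | 0 | 5% | 5% | 5% |
| 0.78 | 0.3 | 7% | 7% | 5% |
| 0.78 | 0.5 | 10% | 10% | 5% |
| 0.78 | 0.78 | 16% | 17% | 5% |
| 0.78 | 1.0 | 22% | 24% | 5% |
| 0.5 | 0.5 | 7% | 7% | 5% |
| 0.3 | 0.3 | 5% | 5% | 5% |
| 0 | 0.78 | 5% | 5% | 5% |

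With the smaller back-solved effect for 30 per arm in the normal approximation (dV = 0.72), the pooled rates at 30 per arm are 9.4%, 14.5% and 21.4% for dM = 0.5, 0.72 and 1.0.

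**4. Scale.** The critical |r| is 0.254 at N = 60 and 0.268 at N = 54. The expected spurious r of 0.05 to 0.16 lies below both, so the bias raises the false-positive rate but does not make a false finding likely in any one test.

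**5. Masking.** Pooling can also hide a real link. With 30 per arm, dV = 0.72, dM = 0.8 and a within-arm correlation of −0.20, the pooled mean r is about −0.05 and the test rejects in 6% of trials; adjusted for arm, mean r is −0.20 and it rejects in 33%.

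**The case against.** Several points on the other side have force.

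- *The SAP does not say the arms are pooled.* Correct. It is silent, and a within-arm analysis is not excluded. For rsfMRI, the grammatical subject of the sentence is the treatment-versus-sham comparison, so arm may be intended. What stands is that an unqualified Pearson correlation is ordinarily run on all patients, and silence leaves the choice open until results are seen.
- *Arm is already in the marker analyses.* A reader might infer that arm is ignored throughout the marker work. Section 6B does not support that: LEP, EEG and rsfMRI are each compared between arms. The gap is confined to the correlations with VAS.
- *A change over the same interval cannot predict the outcome.* This is tempting, but section 7 gives no VAS visit. Correlating a baseline to post-treatment marker change with VAS at 4, 12 or 24 weeks would not be wholly same-interval. The supportable criticism is that the visit is unstated and the term *predictor* is unearned as written.
- *The inflation is modest.* Agreed for small effects, and it is absent if either effect is zero. The rates describe one univariate Pearson test, a method named only for LEP, and do not transfer directly to voxelwise EEG maps.
- *The work is exploratory, and only descriptive statistics are being reported.* The exploratory label covers section 7, not the correlations in 6B or the objective in section 1. The deviation statement at the end of the SAP does limit the present consequence. It also says that ways of resuming are being explored, and a pooled r shown descriptively can mislead without a p-value.

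**Conclusion.** The point holds as an under-specified analysis with a better, nearly free alternative. If the correlations are pooled, and tDCS affects both pain and the marker as the protocol hopes, the plan cannot separate a marker that tracks pain relief from a treatment that moves both. With a VAS effect of 0.78 and marker effects of 0.5 to 1.0, the false-positive rate of a single test is about two to nearly five times nominal; for smaller effects it is 5% to 7%. These figures rest on a back-solved VAS effect, assumed marker effects, normality and zero within-arm correlation. A reader might take 0.78 for the stated design effect, but the SAP states no d.

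Severity is minor to moderate. One of the two objectives depends on these correlations, but the issue bites only if the study resumes or if correlations are shown alongside the descriptive results.

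**What to change.** For each marker actually collected (the protocol's session lists include EEG but not LEP or rsfMRI), state in SAP 6B and 7 that:

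1. the marker–pain association is estimated in a model of VAS on marker change, with arm and baseline VAS as covariates;
2. the arm-adjusted partial correlation is reported with its 95% confidence interval, together with the estimates within each arm;
3. the VAS visit used is named;
4. associations are called correlates, and *predictor* is kept for a marker measured before the pain change it is meant to predict.

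For EEG maps, the same arm term belongs in the voxelwise model. A model with baseline marker by arm interaction is optional: it asks whether the marker modifies the treatment effect, a different question for which the trial was not sized.

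The cost is a few lines of SAP text, one or two degrees of freedom, and possibly a smaller reported correlation. No new data are needed. If only descriptive results are published, any marker–pain plot or coefficient should be shown by arm.
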